8.3.2.1 Patient demographics and other baseline characteristics

Background and demographic characteristics of the full analysis population including age, gender, height, weight, body surface area, tumor type, previous anticancer treatments, medical conditions, performance status etc. will be listed individually by patient, and summarized by dose cohort using descriptive statistics or contingency tables.

8.3.2.2 Study treatment exposure and compliance

The actual dose, duration in days and compliance of BAL101553 treatment will be listed by patient and summarized through descriptive statistics by dose group and treatment cycle in the safety population.

8.3.2.3 Concomitant treatments

Concomitant medications and significant non-drug therapies in the safety population prior to and after the start of the study drug will be listed by patient and summarized by Anatomical Therapeutic Chemical term and by dose group.

8.3.2.4 Dose-limiting toxicity, MAD determination and MTD recommendation

The dose-limiting toxicities will be listed by patient for each dose cohort.

The MAD is defined as the dose level at which DLT are observed during treatment Cycle 1 in \geq two of (up to) three patients with DLT in the first three patients of a dose cohort, or \geq two of (up to) six patients with DLT in a dose cohort that was expanded to six patients and at which dose escalation is being stopped.

The MTD is defined as the highest dose level below the MAD with an acceptable tolerability profile.

The MTD may be different for patients with advanced or recurrent solid tumors and for patients with recurrent or progressive GBM/high-grade glioma.

8.3.2.5 *Objective response rate*

The objective response rate will be calculated within the FAP (Phase 1 portion of the study), as the proportion of patients responding (i.e., with a best observed objective response of complete or partial response, based on RECIST criteria v1.1 for patients with advanced or recurrent solid tumors, CA-125 Rustin criteria for ovarian cancer, or PSA Working Group 2 criteria for prostate cancer); and based on RANO critieria for patients with recurrent or progressive GBM/high-grade glioma.

In the Phase 2a portion of the study (Simon's two-stage design), the patients with measurable disease at baseline in the EEP will be the primary population for the calculation of the objective response rate.

The proportion and its exact 95% confidence interval will be presented by dose cohort and by disease subgroup if appropriate.

8.3.2.6 Disease control rate

The disease control rate will be calculated within the FAP (Phase 1 portion of the study), as the proportion of patients with disease controlled (i.e., complete response, partial response, or stable disease) after two treatment cycles, after four treatment cycles, and at the end of treatment. The proportion and its exact 95% confidence interval will be presented by dose cohort and by disease subgroup if appropriate.

In the Phase 2a portion of the study (Simon's two-stage design), the EEP will be the primary population for the calculation of the disease control rate.

8.3.2.7 Progression-free and overall survival

Progression-free survival is defined as the interval between the date of first study drug administration and the earliest date of objective disease progression according to RECIST criteria v1.1 for patients with advanced or recurrent solid tumors, CA-125 Rustin criteria for ovarian cancer, PSA Working Group 2 criteria for prostate cancer; and based on RANO criteria for patients with recurrent or progressive GBM/high-grade glioma; or Investigator-confirmed clinical progression (see Section 5.6.3); or death due to any cause in the absence of progression. Patients who have not progressed or died at EOS will be censored at the time of their latest objective tumor assessment.

Overall survival is the time from first study drug administration to the date of death / or censored at the time the patient was last known to have been alive.

Progression-free survival will be listed for the FAP (Phase 1 portion of the study) by patient and dose group and by disease subgroup if appropriate.

In the Phase 2a portion of the study (Simon's two-stage design), OS and PFS will be calculated for the FAP and EEP. Median OS and PFS and the proportion of patients with PFS at 6 months after start of study drug treatment (PFS6) will be assessed in the Phase 2a portion of the study (Simon's two-stage design).

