8.3.1.1 Full analysis population

The full analysis population (FAP) includes all patients who received at least one partial or complete dose of study drug, based on the intent-to-treat principle. The FAP will be the primary population for analyzing efficacy in Phase 1.

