8.3.1.4 Pharmacokinetic analysis population

The PK analysis set includes all patients who received at least one dose of study drug and had at least one post-baseline pharmacokinetic assessment.

8.3.1.5 Efficacy-evaluable population (Phase 2a expansion portion of the study, Simon's two-stage design)

The efficacy evaluable population (EEP) is the subset of the FAP who had at least one postbaseline RANO assessment after having received at least 6 weeks of study treatment.

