6.2.3 Progression-free survival

Progression-free survival is defined as the interval between the date of first infusion and the earliest date of objective disease progression according to RECIST criteria v1.1 for patients with advanced or recurrent solid tumors, and based on RANO criteria for patients with recurrent or progressive GBM/high-grade glioma; or Investigator-confirmed clinical progression; or death due to any cause in the absence of progression. Patients who have not progressed or died at EOS will be censored at the time of their latest objective tumor assessment.

If a patient has no post-baseline objective tumor assessment then the PFS will be censored to 0 day.

Progression-free survival will be summarized for the FAP (Phase 1 portion of the study) by disease subgroup and dose cohort.

In the Phase 2a portion of the study (Simon's two-stage design), PFS will be summarized for the FAP and EEP. Median PFS and PFS at 6 months after start of study drug treatment (PFS6) will be assessed in the Phase 2a portion of the study (Simon's two-stage design), using KM method. The 95% CI will be calculated with Brookmeyer-Crowley method. The associated survival curve will be displayed.

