6.2.4 Overall Survival

Overall survival is the time from first study drug administration to the date of death / or censored at the time the patient was last known to have been alive.

Overall survival will be summarized using KM method for the FAP (Phase 1 portion of the study) and the FAP and EEP for the Phase 2a portion of the study (Simon's two-stage design).

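### Phase 2a PFS, PFS6 and OS are planned in two populations with neither primary, and the efficacy-evaluable version carries guarantee-time bias

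*Protocol*

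**What the plan says.** - **Populations.** Protocol 8.3.2.7: "OS and PFS will be calculated for the FAP and EEP". SAP 6.2.3: "PFS will be summarized for the FAP and EEP". SAP 6.2.4 plans OS in "the FAP and EEP for the Phase 2a portion of the study". None of these sections ranks the two sets. Median PFS and PFS6 appear in the same paragraphs.
- **Entry to the EEP.** Protocol 8.3.1.5, repeated in SAP 4.6, takes the FAP patients who "had at least one postbaseline RANO assessment after having received at least 6 weeks of study treatment".
- **Time origin.** Protocol 8.3.2.7 defines PFS as "the interval between the date of first study drug administration and the earliest date of objective disease progression", with clinical progression and death also counting as events. It adds: "Overall survival is the time from first study drug administration to the date of death". SAP 6.2.3 starts PFS at the first infusion; the drug is oral, so I read this as first dose.
- **Where a primary set is named.** Protocol 8.3.1.1: "The FAP will be the primary population for analyzing efficacy in Phase 1". For Phase 2a, Protocol 8.3.2.5 and 8.3.2.6 name EEP-based sets as primary for objective response and disease control. The synopsis assigns the FAP to analyses without specifying them, and the EEP to the evaluation of efficacy.
- **Extra SAP rule.** SAP 6.2.3 censors PFS at day 0 when a patient has no post-baseline tumor assessment.

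**The concern.** Membership of the EEP is decided about six weeks after the clock has started. Those weeks are guaranteed free of death for everyone in the set, and largely free of early treatment-ending progression, yet they count as survival time. This is guarantee-time bias. Neither document applies a landmark or delayed entry to correct it.

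The synopsis lists OS, PFS and PFS6 as the main secondary endpoints, and Protocol 1.5.2.2.1 foresees OS and PFS as primary endpoints in a possible later trial. With no control arm sharing the filter, the bias does not cancel. Two unranked sets of estimates also leave room to feature the more favourable one once the data are known.

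**Working it through.** **1. The plan's own figure.** No expected PFS or OS is given. The nearest figure is Protocol 3.3: about 25% non-evaluable and up to 104 patients enrolled.
- Phase 1 dosed: 26 + 28 = 54. Phase 2a evaluable: 34 + 6 = 40.
- 54 + 40 × 1.25 = 104, which reproduces the total. On this arithmetic 10 of 50, or 20%, are non-evaluable.
- If 25% meant a quarter of those enrolled, the total would be 54 + 40/0.75 = 107.3, which is not 104.

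I carry both 20% and 25%, taking enrolled as treated.

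**2. Formula.** Let L = 6 weeks = 42 days. Suppose patients outside the EEP have left PFS follow-up by L, through an event or censoring, and no EEP member has a PFS event before L. Then for t > L

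S_EEP(t) = S_FAP(t) / S_FAP(L).

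The inflation factor is 1/S_FAP(L). It is never below 1, and exceeds 1 once a single PFS event precedes L.

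**3. Range from the protocol's planning assumption.**

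| Non-evaluable patients | 20% | 25% |
|---|---|---|
| All early PFS events | 1/0.80 = 1.25 | 1/0.75 = 1.33 |
| Half events, half censored; events first | 1/0.90 = 1.11 | 1/0.875 = 1.14 |
| Half events, half censored; censoring first | 1/(1 − 0.10/0.90) = 1.13 | 1/(1 − 0.125/0.875) = 1.17 |
| None early events | 1.0 | 1.0 |

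**4. Exponential PFS, with medians that I assume.** S(t) = 2^(−t/median), six months = 183 days.
- Median 3 months (91.3 days): S(183) = 24.9%, S(42) = 72.7%, so the EEP value is 0.249/0.727 = 34.3%, a factor of 1.38. This needs 27% of patients to have an event before six weeks.
- Median 4 months (121.75 days): S(183) = 35.3%, S(42) = 78.7%, so the EEP value is 44.8%, a factor of 1.27. This needs 21%.

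**5. Scan timing.** Protocol 5.3.2.2 and Table 9 put the first scheduled post-baseline MRI in Days 15 to 28 of Cycle 2, which is study days 28 + 15 = 43 to 28 + 28 = 56. A tumour growing silently in week 3 is normally recorded as progression at that scan, after six weeks of treatment, and stays in the EEP as an event. Step 4 instead removes every event before day 42, as if progression were observed continuously. It therefore lies near or above the upper end of the range in step 3.

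**6. OS.** With exponential survival and exclusion only through death before L, solving S(t)/S(L) = 0.5 gives t = median + L, a shift of 42/30.44 = 1.38 months. For example, an assumed median of 6 months becomes 7.4.

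**7. The FAP as comparator.** SAP 6.2.3 counts death and clinical progression as PFS events, but then censors at day 0 any patient without a post-baseline tumor assessment. Read literally, the second rule removes early deaths and clinical progressions from FAP PFS as well.

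**The case against.** The strongest case against runs as follows, and much of it stands.

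- **Scan timing.** Because the six-week threshold coincides with the opening of the first MRI window, a reader who infers that every progression before six weeks is excluded goes too far. Those lost are early deaths, clinical or unscheduled-scan progressions, other early withdrawals, and patients with no later scan. Treatment may also continue after a mixed response (Protocol 4.4).
- **OS.** A reader might infer that median OS rises by six weeks whatever its true value. That needs both conditions in step 6. EEP entry depends on treatment duration and a scan, and a patient who stops early for toxicity may live long. Eligibility also requires a life expectancy of at least 12 weeks and neurological stability, so a constant hazard from day 1 probably overstates early deaths.
- **Stakes.** Protocol 1.5.2.2.1 names OS and PFS, not PFS6, for a potential later trial. Historical benchmarks are given for response rate only, and no test, threshold or go/no-go rule attaches to PFS, PFS6 or OS. It would be wrong to say that the plan formally judges these endpoints against history.
- **FAP results will exist.** The FAP analysis is already planned alongside the EEP analysis.

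None of this removes the defect. The EEP analysis is prespecified from first dose with no correction, nothing ranks it below the FAP, and the synopsis leans towards it for efficacy.

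**Conclusion.** The concern holds and should be corrected. As written, EEP PFS and PFS6 are biased upward whenever an early death or an early treatment-ending progression occurs. EEP OS is expected to be biased the same way, but this is not certain.

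The size cannot be fixed from the documents. On the protocol's own non-evaluability assumption the PFS6 factor runs from 1.0 (no non-evaluable patient is an early event) to about 1.25 to 1.33 (all are). That assumption is a planning figure, not a bound. The exponential contrasts of 24.9% against 34.3% and 35.3% against 44.8% rest on medians that appear nowhere in the documents and on continuous observation of progression, so they should not be read as the expected bias. A six-week shift in median OS is a special case.

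The FAP is a clean comparator for PFS only if early deaths and clinical progressions count as events despite the day-0 rule. The response-rate design and its error rates are unaffected.

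**What to change.** - In Protocol 8.3.2.7 and SAP 6.2.3 and 6.2.4, name the FAP as the primary population for Phase 2a PFS, PFS6 and OS.
- Drop the EEP version of these endpoints, or start its clock at a six-week landmark and label it supportive.
- In the synopsis, limit the sentence on the EEP to the response endpoints.
- In SAP 6.2.3, state that death or clinical progression without a post-baseline scan is a PFS event in the FAP, and that day-0 censoring applies only to patients with neither.

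The cost is wording. The FAP estimates are already planned, and naming them primary does not change them. The downside for the sponsor is that the more favourable EEP estimates lose their standing. FAP PFS may also come out lower than under a literal reading of the day-0 rule.

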8.3.2.8 Safety data analysis

The assessment of safety will be conducted in the safety population and will be primarily based on the frequency of AEs and laboratory abnormalities. Other safety data (e.g., electrocardiogram, vital signs, special testing) will be considered as appropriate. Safety data will be presented in individual listings and summary tables. Study drug dose interruptions and study drug dose reductions will be presented in individual listings and summary tables.

Adverse events

AEs and SAEs will be described by body system in individual listings and frequency tables for each dose level and cycle as appropriate.

AEs leading to withdrawal or dose modifications will be presented in individual listings and summary tables.

Laboratory evaluations

Laboratory values will be converted into SI units and the severity grade determined based on CTCAE v5.0 whenever applicable.

The frequency of laboratory abnormalities will be displayed by worst CTCAE v5.0 grade and by dose level and cycle as appropriate. Newly occurring CTCAE v5.0 laboratory abnormalities will be displayed in a separate listing. Shift tables will be provided for laboratory parameters classified according to CTCAE v5.0.

Other safety data

Data from other tests (e.g., electrocardiogram) will be listed. Notable abnormalities will be discussed and shift tables provided as appropriate. Vital signs will be listed and summarized using descriptive summary statistics.

8.3.2.9 Pharmacokinetic analysis

All PK parameters will be presented as listings and descriptive summary statistics including arithmetic and geometric means, coefficient of variations, standard deviation, minimum, median and maximum.

A detailed description of the PK analysis will be provided in the 'BAL101553 Pharmacokinetics Manual'.

8.3.2.10 Biomarker analysis

All biomarker parameters will be presented in listings and descriptive summary statistics by cohort and scheduled time point and within disease subgroups, as appropriate.

Analyses of biomarkers and their association to clinical response or pharmacokinetics will be conducted as appropriate and will be exploratory.

8.3.3 Sample size calculation

8.3.3.1 Phase 1 dose escalation portion

The accelerated 3+3 design applied in Phase 1 does not require sample size specification; the escalation is continued until the MAD (i.e., a dose with an unacceptable number of DLT) is observed. The expansion portion is exploratory; therefore, no statistical sample size justification has been applied.

8.3.3.2 Phase 2 dose expansion portion (Simon's two-stage design)

Simon's two-stage design will be used in Phase 2a. The null hypothesis that the true response rate is 14% will be tested against a one-sided alternative. In the first stage, 9 evaluable patients will be accrued. If there are 1 or fewer responses in these 9 patients, the study will be stopped. Otherwise, 10 additional evaluable patients will be accrued for a total of 19. The null hypothesis will be rejected if 6 or more responses are observed in 19 patients. This design yields a type I error rate of 3.7% and power of 81% when the true response rate is 40%.

For actual patient numbers see Section 3.3.

8.3.4 Handling of missing data and discontinuations

Patients whose clinical response is unknown or not reported will be treated as non-responders for summarizing the overall response rate.

Reasons for discontinuation and the date of discontinuation from the study will be listed, and dates of first and last study drug provided as well as the duration of exposure to study drug and date. Summary tables will be provided by dose group.

9 STUDY ADMINISTRATION AND REGULATORY ASPECTS

9.1 Study records

The Investigator must maintain adequate and accurate records to enable the conduct of the study to be fully documented and the study data to be subsequently verified.

Prior to study-specific screening procedures in the Phase 2a portion of the study (Simon's two-stage design), a tissue-screening program adhering to local standards in selected countries will be established to support the identification of potential patients whose GBM tissue is EB1-positive based on IHC. The GBM tissue-testing algorithm is outlined in Appendix 4.

In the context of this tissue screening program, a coded list with GBM tissue samples available for testing will be populated by each study site or the associated pathology laboratory, including confirmation of available patient consent for tissue testing. Each tissue sample provided to the central pathology laboratory for EB1-testing will be tracked with a patient-sample number and confirmation that patient consent for tissue testing is available. The EB1-IHC staining result will be provided by the central pathology laboratory to the study site for each sample, and patients with EB1-positive GBM tissue samples will be approached by the study investigator for potential participation in the study.

In the Phase 2a portion of the study (Simon's two-stage design), patients whose GBM tissue was identified as EB1-positive by IHC as determined by central laboratory testing will be approached by the study investigator to discuss potential study participation, and to initiate the patient information and informed consent process if applicable.

9.1.1 Investigator's study file

The Investigator's Study File must contain all essential documents as required by ICH E6 (R2), e.g., the protocol/amendments, Investigator's Brochure, CRFs and Query Forms, IEC/IRB and governmental approval with correspondence, informed consent forms, patient enrollment and identification logs, drug accountability records, staff curriculum vitae, authorization forms and other appropriate documents/correspondence.

9.1.2 Case report forms

For each patient who signs an informed consent for participation in the study, a CRF must be completed and signed by the Investigator or authorized Sub-investigator. This also applies to records for those patients who fail to complete the study (even during a pretreatment screening period if a CRF was initiated). If a patient withdraws from the study, the reason must be noted on the CRF. If a patient is withdrawn from the study because of a treatment-limiting AE, thorough efforts must be made to clearly document the outcome of the AE.

The Investigator must ensure the accuracy, completeness, legibility, and timeliness of the data reported to the Sponsor in the CRFs and in all required reports.

If the CRF is to be the source document for certain data, this must be discussed and agreed with the Sponsor in advance, and clearly documented.

9.1.3 Patient source documents

Patient source documents used to record key efficacy/safety parameters, independent of the CRFs, may include for example, patient hospital/clinic records, physician's and nurse's notes, appointment books, original laboratory reports, ECG read-outs, X-ray, pathology and special assessment reports, signed informed consent/assent forms, consultant letters, and patient screening and enrollment logs. Source documents are part of the study documents and must be maintained and made available upon request for monitoring visits, audits or inspections.

9.1.4 Document retention and archiving

The Investigator must keep all study documents on file for at least 15 years after completion or discontinuation of the study. Subsequently, the Sponsor will inform the Investigator when the study documents can be destroyed, subject to local regulations.

These files must be made available for inspection, upon reasonable request, to authorized representatives of Sponsor or regulatory authorities.

Should the Investigator wish to assign the study records to another party, or move them to another location, the Sponsor must be notified in advance.

If the Investigator cannot guarantee the archiving requirement at the investigational site for any or all of the documents, arrangements must be made between the Investigator and the Sponsor for appropriate storage.

9.1.5 Sample retention

Blood and tissue samples may be stored for future medical and/or scientific research projects related to BAL101553. All patients will be asked to provide informed consent for this purpose, authorizing the Sponsor to use their study information and samples for future research projects.

9.2 Monitoring

Before study initiation, at a site initiation visit or at an Investigator's meeting, the Sponsor will review the protocol and CRFs with the Investigators and their staff.

The CRA must visit the Investigator and the study facilities on a regular basis throughout the study to verify the adherence to GCP, the protocol and the completeness, consistency and accuracy of the data being entered into the CRFs. The CRA will also ensure that the study drug is being stored, dispensed, and accounted for according to specifications.

The Investigator shall ensure that the monitor has direct access to all required study data (source documents) during the regular monitoring visits. This includes all patient records needed to verify the entries in the CRFs.

The Investigator agrees to cooperate with the CRA to ensure that any deviations or issues detected in the course of monitoring visits are resolved.

